4.3.1.1. Primary analysis

Primary analysis will be done on RS.

Definition: the primary efficacy endpoint is defined as the change from baseline to W013 in ESSDAI total score. The ESSDAI total score is calculated as the weighted sum of 12 items of the scale in ClinTrial database.

Primary analysis: to assess the efficacy of S95011 (750 mg) as compared to Placebo on change from baseline to W013 in ESSDAI total score after a 13-weeks treatment, using a General Linear Model including the fixed, categorical effect of treatment and randomisation stratification factors (rando_factor) as well as the continuous fixed covariate of baseline value. The randomisation stratification factors are baseline intake of oral corticosteroids (yes/no) and baseline intake of antimalarial (yes/no)

GENERAL LINEAR MODEL: $change = baseline + rando_factors + treatment$ [1]

The assumptions underlying the model, as for instance, the normality and homoscedasticity of residuals and detection of outliers will be checked. The assumptions of normality and homoscedasticity of residuals will be investigated using some graphs and descriptive statistics. The detection of outliers will be done using graphics.

If the model is not running due to too few patients in the stratas, the model mentioned above will be modified. Thus, the two stratification factors in the model will be replaced by the following composite factor: baseline intake of oral corticosteroids or antimalarial or both (yes/no). If the model is still not running with the stratification factor in two classes, then the stratification factor will not be considered.

Statistical hypotheses:

Let μ_0 and μ_1 be the population means of the change from baseline in ESSDAI total score at W013 (primary endpoint) under placebo and S95011, respectively.

The statistical hypotheses that will be tested are:

$$H_0: \mu_0 \geq \mu_1 \text{ (S95011 is not superior to placebo)}$$

versus

$$H_1: \mu_0 < \mu_1 \text{ (S95011 is superior to placebo)}$$

The type I error of the statistical tests will be set at 10% for unilateral situation, which is consistent with the objective of demonstrating the superiority versus placebo.

Missing data/intercurrent events handling: the primary analysis for the primary estimand will be conducted using only data obtained prior to IEs. Observed post IE values will not be used in the primary analysis. Post IE values will be imputed according to the MAR assumption (multiple imputation by treatment group). This is aligned with the primary estimand and the hypothetical strategy. Missing data not linked to intercurrent events will be imputed according to the MAR assumption with a multiple imputation by treatment group. The imputation method is detailed below and in [Appendix 7.3.1](#). A patient with all visits missing or only baseline missing will not be considered in the analysis.

Multiple imputation inference involves 3 consecutive phases.

1/ Imputation step:

A total of 100 imputed complete data sets will be generated.

The imputation step for missing data as well as data considered as missing for the primary analysis due to the strategy used to handle intercurrent event will be the same and applied to data with a monotone pattern. For all patients, the regression method (adjusted on randomisation stratification factors, baseline and considering all longitudinal data of planned visits) will be used separately for each treatment arm to impute missing data (*i.e.* based on patient completers under corresponding treatment arm) under MAR approach.

It is of note that for missing data with an arbitrary missing pattern, the first imputation step might be preceded by one MI approach based on MCMC method using baseline and all longitudinal data by treatment groups.

If the regression method for imputation is not running due to too few patients in the stratas, the model mentioned above will be modified. Thus, the two stratification factors in the model will be replaced by the following composite factor: baseline intake of oral corticosteroids or antimalarial or both (yes/no). If the model is still not running with the stratification factor in two classes, then the stratification factor will not be considered.

2/ Analysis step:

The same model as [1] (described above) will be applied to each of the 100 imputed datasets.

3/ Combination step:

Statistical inferences will be generated by combining results from the 100 analyses using Rubin's formulae. The multiple imputation estimator of the difference between S95011 and placebo is the average of the individual 100 estimators. The variance of the estimator is the combination of the between- and within-imputation variability ([Carpenter and Kenward, 2007](#)).

Multiplicity handling: there is no multiplicity issue.

Statistical elements: Finally, the following elements will be provided in a summary table:

- Estimate (standard error) of the difference between adjusted treatment arm means.
- Two-sided 80% CI of the estimate.
- Two-sided 95% CI of the estimate.
- One-sided p-value.

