3.1. Primary objective

The primary objective of the study is to assess the effect of multiple intravenous infusions of 750 mg of S95011 compared to placebo after 13 weeks of treatment in reducing disease activity using EULAR Sjögren Syndrome Disease Activity Index (ESSDAI).

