1.2. Determination of sample size

The following efficacy criteria are defined:

- A statistically significant reduction in ESSDAI at W013 in the S95011 group compared to placebo, at the one-sided 10% significance level.
- An estimated mean reduction in ESSDAI in the S95011 group to be 3 points or greater than placebo. The decrease of 3 points was chosen because it is considered as clinically minimal relevant decrease ([Seror et al, 2016](#)).

Targeted sample size

With 45 patients in the primary analysis of the primary estimand (30 in the S95011 group and 15 in the placebo group), the study would have around 5% chance of having a false-positive result, *i.e.*, of meeting both the efficacy criteria when the true difference between S95011 and placebo is zero. Additionally, the chances of meeting both the efficacy criteria remain below 14% for true differences between S95011 and placebo of less than 1 point.

The study would have approximately 70% chance of meeting both the efficacy criteria, when the true difference between S95011 and placebo is 4 points. In case the true difference between S95011 and placebo is only 3 points, the study would have approximately 50% chance of meeting both the efficacy criteria. These calculations assume that the primary efficacy endpoint, change from baseline in ESSDAI, follows a normal distribution with a standard deviation of 6. This estimate of the standard deviation is based on some clinical studies (Fisher *et al*, 2020, UCB5857, RO5459072) in patients with primary Sjögren's syndrome in which the observed standard deviation ranged from around 4 to 6.

Blinded standard deviation reassessment

The similar operational characteristics (false-positive and right-positive rates) are obtained with 20 patients in S95011 group and 10 patients in placebo group under assumption of an overall standard deviation of primary efficacy endpoint of 5. So only if the recruitment is much longer than expected, when 30 patients will have completed the 13-week treatment period, the overall standard deviation of the primary endpoint on non-comparative data could be calculated. If the value is less or equal to 5, the sponsor could stop the patient recruitment, considering that the number of patients is sufficient to meet both efficacy criteria. This potential adaptation has very little or no impact on the probability of having a false-positive result (Kieser, 2003).

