3.2. General definitions

Patients having taken at least one dose of IMP correspond to patients with at least one date of first and/or last IMP intake complete or partially complete.

Analysable value will be defined as any non-missing value, except for:

- Laboratory parameters:
 - A laboratory value is considered as analysable if non-missing and not flagged in the ClinTrial database as "not analysable".
 - Vital signs value is considered as analysable if collected under appropriate circumstances (corresponds to the item of the source database).

Baseline value will be defined as the last analysable value prior to the first IMP intake. In case of patient included and/or randomised but not having taken at least one dosage of IMP: value at baseline is defined as the last analysable value prior or equal to date of inclusion visit.

Considered periods are:

- ASSE-W013 period.
- ASSE-W028 period.

Last post-baseline value under treatment of the period will be defined as the last post-baseline analysable value under treatment during the considered period.

Change from baseline to post-baseline visit is calculated as: Value at the post-baseline visit - Value at baseline.

Change from baseline to post-baseline visit under treatment is calculated as: Value at the post-baseline visit under treatment - Value at baseline.

Change from baseline to last post-baseline value under treatment is calculated as: Last post-baseline value under treatment - Value at baseline.

For safety endpoints (except adverse events), the following definition will be applied:

- **High emergent abnormal value under treatment according to the laboratory reference ranges** is defined as value \leq ULN (Upper Limit of Normal laboratory reference range) or missing at the baseline of the treatment period and $>$ ULN under treatment.
- **Low emergent abnormal value under treatment according to the laboratory reference ranges** is defined as value \geq LLN (Lower Limit of Normal laboratory reference range) or missing at baseline of the treatment period and $<$ LLN under treatment.

- **High emergent abnormal value under treatment according to the cut-offs for PCSA** values is defined as value \leq ULS (Upper Limit used to define potentially clinically Significant abnormal values) or missing at baseline of the treatment period and $>$ ULS under treatment.

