4.1.3. Demographic data and baseline characteristics

Demographic characteristics and other baseline characteristics will be summarized as follows, by treatment group and overall, in the RS:

- Demographic characteristics:
 - Age (years).
 - Sex: male / female.
 - Race: White / American Indian or Alaska Native / Asian / Black or African American / Native Hawaiian or other Pacific Islander / Other.
 - Ethnicity: Hispanic or Latino / not Hispanic or Latino.
 - Life habits:
 - Smoking (excluding e-cigarette): Never / Has stopped smoking / Current smoker.
 - E-cigarette: Yes / No.
 - Alcohol: No / Has stopped drinking / Currently drinking.
 - Caffeine: Yes / No.
- Baseline characteristics:
 - History of the primary Sjögren's syndrome:
 - Disease duration (years) and by class: ≤ 7 years / > 7 years.
 - Specific treatment for pSS for which a stratification was done at baseline Nothing / Oral corticosteroid / Antimalarial / Oral corticosteroid and antimalarial.
 - Relevant medical and surgical history other than the PSS symptoms (by SOC and PT).
 - Specific previous treatment (by ATC code and preferred name).
 - Non-specific previous treatment (by ATC code and preferred name).
 - ESSDAI total score overall and in severity classes: Mild < 5 / Moderate [5 – 14[/ Severe ≥ 14 .

- ESSDAI by domain: Constitutional / Lymphadenopathy and lymphoma / Glandular / Articular / Cutaneous / Pulmonary / Renal / Muscular / PNS / CNS / Haematological / Biological.
- ESSPRI total score overall and in classes: $< 5 / \geq 5$.
- ESSPRI by symptom: Dryness / Fatigue / Pain.
- SF-36 physical and mental scores.
- MFI by domain: General fatigue / Physical fatigue / Reduced activity / Reduced motivation / Mental fatigue.
- NRS: PhGA score and PGA total score.
- Schirmer test for the most affected eye and mean of both eyes.
- OSS for the most affected eye and mean of both eyes.
- Sialometry (stimulated and unstimulated salivary flow score).
- Weight (kg).
- Body temperature (°C).
- BMI (kg/m²) and by class: < 18.5 , $[18.5-25[$, $[25-30[$, ≥ 30 .
- SBP (mmHg).
- DBP (mmHg).
- HR (b.p.m).

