4.3.6. Additional estimands based on other efficacy endpoints

These estimands of interest are the effect of the treatments on global assessments of the disease activity reported by the physician (PhGA) and by the patient (PGA), and tear and salivary glands function (Schirmer test, OSS and salivary test), in all patients assuming non-occurrence of IEs. The motivation for this choice is the same as the primary estimand.

The attributes of these estimands are defined as follows:

- **Treatment:** S95011 or placebo.
- **Population:** RS.
- **Variable 1:** change in PhGA score from baseline to W013.
- **Variable 2:** change in PGA total score from baseline to W013.
- **Variable 3:** change in Schirmer test from baseline to W013 (on the most affected eye and mean of both eyes).
- **Variable 4:** change in OSS from baseline to W013 (on the most affected eye and mean of both eyes).
- **Variable 5:** change in unstimulated salivary flow score from baseline to W013.
- **Summary measure:** difference in means between treatments.
- **Intercurrent events (IE):**
 - IE1: Study drug discontinuation for major worsening of primary Sjögren's syndrome.
 - IE2: Increase or initiation of authorized medication for pSS.

- IE3: Study drug discontinuation for AE related to study drug.
- IE4: Study drug discontinuation for other reasons (non-medical reason, AE not related...).
- IE5: Switch of treatment group (error of dispensation).
- IE6: Decrease or stop of authorized medication for pSS.

Note: In case a patient is concerned by several IEs, the first event will be considered. If several IE occurred the same day, IE will be considered to be more conservative in the following order: IE1; IE2; IE3; IE4; IE5, IE6. Main analyses are the same as for the primary estimand. Sensitivity and supplementary analyses are not planned for these estimands.

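### The one-sided primary hypotheses are printed the wrong way round in both documents: as written, the test calls S95011 superior when ESSDAI changes less favourably than on placebo

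*SAP*

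**What the plan says.** SAP 4.3.1.1 defines mu_0 and mu_1 to "be the population means of the change from baseline in ESSDAI total score at W013 (primary endpoint) under placebo and S95011, respectively". The null is "H_0: \mu_0 \geq \mu_1 \text{ (S95011 is not superior to placebo" and the alternative is "H_1: \mu_0 < \mu_1 \text{ (S95011 is superior to placebo". Protocol 10.1.2.4.1.1 gives the same definitions and inequalities. The test is one-sided at 10%.

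On the sign of a change, SAP 3.2 says: "Change from baseline to post-baseline visit is calculated as: Value at the post-baseline visit - Value at baseline". On the direction of the scale, SAP 4.1.3 classes baseline ESSDAI as "Mild < 5 / Moderate [5 – 14[/ Severe ≥ 14", so higher is worse. Protocol 3.1 states the aim as the effect "after 13 weeks of treatment in reducing disease activity using EULAR Sjögren Syndrome Disease Activity Index (ESSDAI".

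SAP 1.2 and protocol 10.2 set two efficacy criteria. The first is "A statistically significant reduction in ESSDAI at W013 in the S95011 group compared to placebo, at the one-sided 10% significance level". The second is an estimated reduction at least 3 points greater than on placebo.

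For PhGA, PGA, Schirmer, OSS and unstimulated salivary flow, SAP 4.3.6 says: "Main analyses are the same as for the primary estimand".

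**The concern.** A more negative change is the better outcome, so superiority of S95011 requires mu_1 < mu_0. The printed alternative is the opposite, and the printed null contains every true benefit. The labels in brackets contradict the inequalities beside them.

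For a two-sided test this would be cosmetic. Here the p-value is one-sided and the first efficacy criterion rests on it. No other passage fixes the tail: the list of outputs in SAP 4.3.1.1 asks only for a one-sided p-value, and SAP 7.3.1 sets up a contrast equal to zero with a two-sided interval. SAP section 6, which lists changes from the protocol, does not correct the direction.

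A programmer who follows the inequality produces an inverted p-value. One who silently reverses it departs from the stated hypothesis, and a tail chosen after unblinding invites challenge.

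The gap extends to other endpoints. SAP 4.3.6 mixes endpoints where lower is better (PhGA, PGA, OSS) with endpoints where higher is better (Schirmer, salivary flow). The responder analyses in SAP 4.3.1.3 also report a one-sided p-value, and there a higher proportion is better. No single direction serves all of these.

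**Working it through.** **Inputs** (SAP 1.2, also protocol 10.2): 30 patients on S95011, 15 on placebo, SD 6, one-sided alpha 10%, and a 3-point threshold for the second criterion. Write b = mu_0 - mu_1 for the true benefit, positive when S95011 is better.

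**Standard error.** SE = 6 × sqrt(1/30 + 1/15) = 6 × sqrt(0.1) = 1.897.

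**Reproducing the plan's own figures, in the benefit direction.** Significance needs an observed benefit of at least 1.2816 × 1.897 = 2.43. The second criterion needs 3, so 3 is the binding threshold and P(both criteria) = 1 - Phi((3 - b)/1.897).

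| True benefit b | Plan states | Computed |
|---|---|---|
| 0 | around 5% | 5.7% |
| 1 | below 14% for less than 1 point | 14.6% at exactly 1 |
| 3 | approximately 50% | 50.0% |
| 4 | approximately 70% | 70.1% |

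All agree within 2 percentage points, so the sample size was worked out with benefit as a greater reduction on S95011.

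**Both criteria under the printed hypotheses.** Rejection needs an observed S95011-minus-placebo difference above about +2.43. The second criterion needs that difference to be -3 or lower. Both cannot happen, so the probability of meeting the two criteria is zero whatever the true effect. The plan's figures cannot come from the printed direction.

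**The significance test alone.** Non-central t with 30 + 15 - 2 = 43 df and one-sided critical value 1.302. The non-centrality is -b/1.897 for the printed direction and +b/1.897 for the intended one.

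| True benefit b | P(reject), as printed | P(reject), intended |
|---|---|---|
| 4 (better) | 0.04% | 79.0% |
| 3 (better) | 0.2% | 61.2% |
| 1 (better) | 3.6% | 22.4% |
| 0 | 10% | 10% |
| -3 (worse) | 61.2% | 0.2% |
| -4 (worse) | 79.0% | 0.04% |

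**The p-value from given data.**
- Observed difference -4: t = -4/1.897 = -2.11 on 43 df. The lower tail gives p = 0.020; the printed direction gives p = 0.980.
- Observed difference -3 (normal approximation): p = 0.057 as intended and 0.943 as printed.

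**Direction of the other endpoints.** In the STAR definition (SAP 7.2.2.4), improvement is an increase in Schirmer or unstimulated salivary flow and a decrease in OSS. PhGA and PGA run from inactive to very active disease (protocol Appendix 6), so lower is better. A test carried over from the primary analysis would need opposite tails for these two groups, and the SAP does not say so.

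**The case against.** The strongest reply is that this is a slip of notation and that nobody could mistake the intent. The bracketed labels, the objective and both efficacy criteria all point to a reduction, and the sample-size figures reproduce only in that direction. That is right, and the most likely explanation is a drafting error.

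It can also be said that the practical damage is bounded:

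- A harmful drug could not meet both criteria, because the second needs an observed reduction at least 3 points greater than placebo. This stands. The 79% for a harmful drug describes the significance test alone.
- The estimate, its standard error and the two-sided 80% and 95% intervals do not depend on the printed direction. The 80% interval carries the intended decision, since its upper bound lies below zero exactly when the first criterion is met in the intended direction. This stands too.
- The protocol gives no arithmetic for change. Read as improvement, its inequality would be correct. That holds for the protocol taken alone, but SAP 3.2 rules the reading out for the analysis that will be run.
- The hypotheses name ESSDAI only, so carrying them into SAP 4.3.6 is an inference; the cross-reference may mean only the model and the imputation. Fair. What remains is that the tail is not stated for endpoints that report a one-sided p-value and where higher is better.

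These points limit the consequence. They do not make the printed hypotheses correct, and clear intent elsewhere does not supply the missing definition of the p-value.

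**Conclusion.** The concern holds. Read with the SAP's definition of change, the primary null and alternative are reversed in both documents, and the test as printed cannot show a benefit: under any true benefit it rejects less than 10% of the time, and then only on data favouring placebo. At the design values, a true 4-point benefit is detected with probability 0.04% instead of 79%, and the two efficacy criteria become mutually exclusive.

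These figures assume an unadjusted two-group comparison at the planned size and SD, without covariates or imputation, and a programmer who follows the inequality and not its label. They describe what the text specifies and do not predict what the sponsor would do. Because the formal hypothesis of the primary test is inverted and the correction costs almost nothing, it must be fixed.

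**What to change.** In SAP 4.3.1.1 and protocol 10.1.2.4.1.1, restate the hypotheses as H0: mu_1 >= mu_0 against H1: mu_1 < mu_0, keeping the labels. Add one sentence defining the one-sided p-value as the lower-tail probability for S95011 minus placebo, and repeat it in SAP 7.3.1, where the contrast is specified.

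State the tail for every other endpoint with a one-sided p-value:
- **Lower tail:** ESSDAI in the sensitivity and treatment-policy analyses, ESSPRI, PhGA, PGA and OSS.
- **Upper tail:** Schirmer, salivary flow and all responder proportions.

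Record the correction in SAP section 6. The cost is wording in two documents. No change to the design, sample size, model or data collection is needed. It should be made before unblinding so that the tail is fixed in advance.

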4.3.1.2. Sensitivity analyses

Sensitivity analysis will be done on RS.

Sensitivity analysis: the same analysis as the primary analysis will be performed using model [1] except the fact the missing data/ intercurrent event handling will be different.

Missing data/intercurrent events handling: in order to assess the sensitivity to the missing at random (MAR) assumption, values post the following IEs:

- IE1: Study drug discontinuation for major worsening of primary Sjögren's syndrome.
- IE2: Increase or initiation of authorized medication for pSS.
- IE3: Study drug discontinuation for AE related to study drug.

will not be taken into account and will be imputed according to the missing not at random (MNAR) assumption.

The other IEs and missing data will be handled as in the primary analysis. The imputation method is detailed below and in [Appendix 7.3.2](#). A patient with all visits missing or only baseline missing will not be considered in the analysis.

Note: In case a patient is concerned by several IEs, the first event will be considered. If several IE occurred the same day, IE will be considered to be more conservative in the following order: IE1; IE2; IE3; IE4; IE5, IE6. Multiple imputation inference involves 3 consecutive phases.

1/ Imputation step:

A total of 100 imputed complete data sets will be generated.

The imputation step for missing data with a monotone pattern will be:

- For all data following study drug discontinuation for major worsening of primary Sjögren's syndrome (IE1), the values of outcome will be imputed using a reference based multiple imputation ("jump to placebo" approach) for S95011 group and using multiple imputation (MAR) for the placebo group. This approach assumes that patients from S95011 mean's response distribution is that of the placebo group patients ([Carpenter et al, 2013](#)). The imputed value will reflect the fact that these IEs are considered a bad outcome (worst case scenario).
- For all data following increase or initiation of authorized medication for pSS (IE2) or study drug discontinuation for AE related to study drug (IE3), the values of outcome will be imputed using a reference based multiple imputation ("copy increments in placebo" approach) for S95011 group and using multiple imputation (MAR) for the placebo group. This approach assumes that patients from S95011 will exhibit an evolution of the disease similar to patients in the placebo group but starting from the benefit already obtained ([Carpenter et al, 2013](#)). The imputed value will reflect the fact that these IEs are considered a moderately bad outcome.
- For all data following another type of IE or missing data due to other reason, imputation will be done as in the primary analysis.

It is of note that for missing data with an arbitrary missing pattern, the first imputation step might be preceded by one MI approach based on MCMC method using baseline and all longitudinal data by treatment groups. If a patient has missing data before an intercurrent event, all data of this patient will be imputed using the method according to the intercurrent event.

2/ Analysis step:

The same model as [1] (described above) will be applied to each of the 100 imputed datasets.

3/ Combination step:

Statistical inferences will be generated by combining results from the 100 analyses using Rubin's formulae. The multiple imputation estimator of the difference between S95011 and placebo is the average of the individual 100 estimators. The variance of the estimator is the combination of the between- and within-imputation variability ([Carpenter and Kenward, 2007](#)).

Multiplicity handling: there is no multiplicity issue.

Statistical elements: Finally, the following elements will be provided in a summary table:

- Estimate (standard error) of the difference between adjusted treatment arm means.
- Two-sided 80% CI of the estimate.
- Two-sided 95% CI of the estimate.
- One-sided p-value.

